11.6.2.2 Handling of Partial Dates

Element	Reporting Detail
Concomitant Medications	
 Partial dates for any concomitant medications recorded in the CRF will be imputed using the following convention: 
 If the partial date is a start date, a '01' will be used for the day and 'Jan' will be used for the month If the partial date is a stop date, a '28/29/30/31' will be used for the day (dependent on the month and year) and 'Dec' will be used for the month. The recorded partial date will be displayed in listings.
Adverse Events	
 Any partial dates for adverse events will be raised to data management. If the full date cannot be ascertained, the following assumptions will be made: 
 If the partial date is a start date, a '01' will be used for the day and 'Jan' will be used for the month. However, if this results in a date prior to Week 1 Day 1 and the event could possibly have occurred during treatment from the partial information, then the Week 1 Day 1 date will be assumed to be the start date. The AE will then be considered to start on-treatment (worst case). If the partial date is a stop date, a '28/29/30/31' will be used for the day (dependent on the month and year) and 'Dec' will be used for the month. The recorded partial date will be displayed in listings.

11.6.2.3 Handling of Missing Data for Statistical Analysis

The SAS PROC MCMC framework automatically assumes/implements a missing at random / multiple imputation approach if any of the supplied response variables are missing. This is deemed to be sufficient given the exploratory nature of the study. However, if a large proportion of data are missing then alternative approaches may be considered.

Several analyses are specified as being conditional on there being sufficient non-missing data to take place (e.g. Sputum and biomarkers with large proportions of LLQ values).

If model covariates are missing (e.g. Baseline) then the best approach will be selected on a case by case basis, but may involve omitting the record or imputing a response based on other data prior to fitting the observation model.

Given the exploratory nature of this study and the large number of endpoints it is not possible to pre-specify/cover all eventualities but any missing data approaches investigated would be documented in the CPSR and if deemed important included in the outputs as sensitivity analyses.

11.7 Appendix 7: Values of Potential Clinical Importance

11.7.1 Laboratory Values

Hematology Analyte	Effect	Relative – Low (Multipliers of LLN)	Relative – High (Multipliers of ULN)
White Blood Cell Count		0.67	1.82
Neutrophil Count		0.83	
Lymphocytes		0.81	
Hemoglobin	Male		1.03
	Female		1.13
Hematocrit	Male		1.02
	Female		1.17
Platelet Count		0.67	1.57
		Absolute – Low	Absolute – High
MCV (fL)		< 80	> 100
MCH (pg/cell)		< 25.78	> 34
Monocytes (K/mL)		< 0.1	> 0.9
Eosinophils (K/mL)		< 0	> 0.6
Basophils (K/mL)		< 0	> 0.9

Chemistry Analyte	Effect	Relative – Low (Multipliers of LLN)	Relative – High (Multipliers of ULN)
Albumin (mmol/L)		0.86	
Calcium (mmol/L)		0.91	1.06
Glucose (mmol/L)		0.71	1.41
Potassium (mmol/L)		0.86	1.10
Sodium (mmol/L)		0.96	1.03

Liver Function			
Test Analyte	Units	Category	Clinical Concern Range
ALT/SGPT	U/L	High	$\geq 2 \times \text{ULN}$
AST/SGOT	U/L	High	$\geq 2 \times \text{ULN}$
Alkaline Phosphatase	U/L	High	$\geq 2 \times \text{ULN}$
Total Bilirubin	$\mu\text{mol/L}$	High	$\geq 1.5 \times \text{ULN}$
Total Bilirubin + ALT	$\mu\text{mol/L}$	High	$1.5 \times \text{ULN}$ Total Bilirubin
			+
	U/L		$\geq 2 \times \text{ULN}$ ALT

Note: The following lab tests are being collected in this study but have not had PCI ranges defined: RBC Count, BUN, Creatinine, Direct Bilirubin and Total Protein. The maximum and minimum observed values will be reported as part of the lab summary tables and this is deemed sufficient to identify potentially extreme values which would then be investigated further if required.

11.7.2 ECG

ECG Parameter	Units	Clinical Concern Range	
		Lower	Upper
Absolute			
Absolute QTc Interval	msec		> 450
Absolute PR Interval	msec	< 110	> 220
Absolute QRS Interval	msec	< 75	> 110
Change from Baseline			
Increase from Baseline QTc	msec		> 60

11.7.3 Vital Signs

Vital Sign Parameter (Absolute)	Units	Clinical Concern Range	
		Lower	Upper
Systolic Blood Pressure	mmHg	< 85	> 160
Diastolic Blood Pressure	mmHg	< 45	> 100
Heart Rate	bpm	< 40	> 110
Body Temperature	°C	< 36.0	> 37.5

Vital Sign Parameter (Change from Baseline)	Units	Clinical Concern Range			
		Decrease		Increase	
		Lower	Upper	Lower	Upper
Systolic Blood Pressure	mmHg	≥ 20	≥ 40	≥ 20	≥ 40
Diastolic Blood Pressure	mmHg	≥ 10	≥ 20	≥ 10	≥ 20
Heart Rate	bpm	≥ 15	≥ 30	≥ 15	≥ 30
		Clinical Concern Range			
		Lower		Upper	
Body Temperature	°C	< -1		> +1	

11.8 Appendix 8: Multicentre Studies

11.8.1 Methods for Handling Centres

- See Section 11.9.1 for details of how centres will be handled in the statistical modelling.

11.9 Appendix 9: Examination of Covariates, Subgroups & Other Strata

11.9.1 Handling of Covariates, Subgroups & Other Strata

- The following is a list of covariates that may be used in descriptive summaries and statistical analyses, some of which may also be used for subgroup analyses.
- Additional covariates of clinical interest may also be considered.
- If the percentage of subjects is small within a particular subgroup, then the subgroup categories may be refined prior to unblinding the trial.
- If the category cannot be refined further, then descriptive rather than statistical comparisons may be performed for the particular subgroup.
- To avoid parameter estimation problems caused by the small sample size (i.e. empty cells in the possible combinations of centre, treatment and allergen exposure) the default approach (unless specified otherwise) for fitting centre in statistical models is to handle it as a random effect (Normally distributed with mean zero and a SD appropriate to the endpoint). Where possible historical data would be used to form a weakly informative prior for the SD, with the specific value described in the corresponding RAP section. If historical data are not available then the distribution for the random centre effects would use a SD value of 1000.
- For analyses without repeated measures over visit, the output from fitting three nested models (M1-M3) to each statistical analysis should be available (e.g. listing form); but inferences (summary tables and figures) would be produced from the final chosen model only. The three models represent possible combinations of centre (fitted as a random effect), treatment and allergen exposure status (fitted as fixed effects). The models may include other terms appropriate to the analysis, but any further covariate exploration activity would start using the selected model (M1, M2 or M3) as its base:
 - **M1:** Centre + Treatment + Allergen Exposure + Treatment*Allergen Exposure + <other terms>
 - **M2:** Centre + Treatment + Allergen Exposure + <other terms>
 - **M3:** Centre + Treatment + <other terms>

Where Treatment = “Placebo” or “20ng GSK2245035”, Allergen Exposure = “Presumed allergen” or “Unknown allergen” and Centre is the random effect drawn from the $N(0, SD)$ distribution.
- The DIC criteria (which may be overruled by expert judgement) would be used to select from Models M1-M3 (see Section 11.11.1). To aid review DIC values from models M1 to M3 should also be summarised in one location in the listing. Examples of expert judgement would be rejecting model M1, even if the DIC

suggested otherwise, if the effect size was deemed to be too small to be clinically important/relevant (i.e. differences in the point estimates for the presumed and unknown allergen exposure responses are clinically unimportant). Other examples of expert judgement include making an overarching decision on the model structure based on all endpoints of a similar nature (e.g. choosing a model form (M1, M2 or M3) for both primary endpoints, or for all serum biomarkers measuring TLR7 induction).

- An analogous set of three models should be used when comparisons of treatment within multiple visits are of interest:
 - **R1:** Centre + Treatment + Visit + Allergen Exposure + Treatment*Visit + Allergen Exposure*Visit + Treatment*Allergen Exposure + Treatment*Allergen Exposure*Visit + <other terms>
 - **R2:** Centre + Treatment + Visit + Allergen Exposure + Treatment*Visit + Allergen Exposure*Visit + <other terms>
 - **R3:** Centre + Treatment + Visit + Treatment*Visit + <other terms>
- If any of the models M1-M3 (or R1-R3) cannot be fitted then the formal process to select models described above is not possible and the default approach should be to use the simplest model form that has acceptable model convergence.

Category	Covariates and / or Subgroups
Centre	One level per site contributing evaluable data to the analysis. Sites may be grouped by country for display purposes. If pooling of centres is deemed necessary the strategy would be to pool centres within the same country before attempting to pool centres over different countries.
Country	Currently planned to be either "UK" or "Germany" but other countries may be utilised.
Allergen Exposure	"Presumed allergen" or "Unknown allergen"
Blood Eosinophil Levels (Cells/mL)	Although the planned statistical modelling will fit this term as a continuous covariate the following categorical variables may be derived based on 
 i) Baseline (SV2) Blood Eosinophils: <150 Cells/mL and >= 150 Cell/mL ii) BAC visit Blood Eosinophil Levels: <150 Cells/mL and >= 150 Cell/mL
Sputum Eosinophil Levels (%) Note: Only if data are available	Although only derivable for subjects/timepoints where sputum samples were produced and were viable the following variables should be created for use as potential categorical covariates based on 
 i) Baseline (SV2) Sputum Eosinophils: <= 2% and > 2% ii) BAC visit Sputum Eosinophils: <= 2% and > 2% iii) Baseline (SV2) Sputum Eosinophils: <= Median of Observed values and > Median of Observed values

Category	Covariates and / or Subgroups
	iv) BAC visit Sputum Eosinophils: <= Median of Observed values and > Median of Observed values
FeNo (Ppb)	Potential categorical covariate based on i) <= 25 ppb and > 25 ppb

11.10 Appendix 10: Multiple Comparisons & Multiplicity**11.10.1 Handling of Multiple Comparisons & Multiplicity**

Due to the extensive use of a Bayesian framework and the early phase / exploratory medicine nature of this study there will be no explicit multiplicity adjustments.

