
 • Each endpoint will be analysed separately using a Bayesian Mixed effects model fitted within Proc MCMC in SAS using the following approach: • Assume equal variances across treatment arms and use a pooled estimate of residual variability (Note: if the posterior predictive distributions produced to support the interim analysis suggest this assumption may be invalid then the modelling approach may be modified to estimate separate variance terms for each treatment arm). • Step 1: Fit all three of the following models (report output from each model in the same listing – along with the DIC values and changes in DIC values between models). Using a combination of changes in the DIC criteria, and expert judgment (see Section 11.9.1), select a single model. 
 • M1: Intercept + Centre + Treatment + Allergen Exposure + Treatment*Allergen Exposure + Baseline • M2: Intercept + Centre + Treatment + Allergen Exposure + Baseline • M3: Intercept + Centre + Treatment + Baseline • See Section 11.4.2 for Baseline definitions (Screening visit 2 BAC endpoint).

Primary Statistical Analyses

Where in each of the models (M1, M2 and M3) the effects are:

Type	Name (#Levels)	Parameters	Prior(s)
Fixed Categorical	Intercept (1)	#1 Intercept	N (0, Var=1E6)
	Treatment (2)	#1 Placebo	N (0, Var=1E6)
		#2 20ng	n/a (constraint = 0)
	Allergen Exposure (2)	#1 Presumed	N (0, Var=1E6)
		#2 Unknown	n/a (constraint = 0)
	Treatment * Allergen Exposure (4)	#1 Pbo*P	N (0, Var=1E6)
		#2 Pbo*U	n/a (constraint = 0)
		#3 20ng*P	n/a (constraint = 0)
		#4 20ng*U	n/a (constraint = 0)
Fixed Continuous*	Baseline	Baseline slope	N(0, Var=1E6)
Random	Centre (planned 6 centres)	Separate value per contributing centre sampled as i.i.d $\sim N(0, \sigma_{Centre}^2)$	$\sigma_{Centre}^2 \sim \text{Gamma}(\text{Shape}=0.048, \text{Scale}=0.830)$ Weakly informative prior based on 6x in-house GSK datasets – same prior for both endpoints Δ

*=Centre covariates prior to fitting model (do not use observations that will not contribute to the planned model when centering) and if applicable the centering is to occur after any transformations have been applied

Δ =If chain is not mixing (i.e. sticking at values close to zero) an additional mixture prior may be considered to act as a lower boundary constraint, or the centre term excluded from the model.

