- Assuming that the final model is not of the “R1” form (See Section [11.9.1](#)) then treatment comparisons of interest are the equivalents to the frequentist counterpart LSMeans estimates for Treatment*Visit in a model fitted in SAS PROC MIXED. The posterior distributions of these quantities will be obtained and the median and 95% credible interval (equi-tail) will be tabulated and displayed graphically. Additionally, appropriate combinations of model parameters will be constructed to obtain the posterior distributions of the ratio of Active / Placebo for each planned time point (equivalent to extracting out relevant back transformed LSmean diffs from a PROC MIXED call for a log-transformed response variable). The posterior probabilities that the ratios at each planned timepoint exceeded the cut-points described [Table 14](#) will be computed, along with the median and 95% credible interval (equi-tail) of the distribution. The posterior distributions for the ratios will be displayed graphically and the aforementioned items tabulated. Note: These posterior probabilities relate to events in the current study, and the mean responses on the treatment arms. Predictions relating to i) an individual subject in a future trial and ii) the mean response in a future trial with N subjects per arm will not be produced as part of the reporting of this study, but may be obtained as part of experimental design activities for any future clinical trials involving GSK22454035.
- If the model is of the “R1” form (See Section [11.9.1](#)) then the approach will be modified to obtain and display LSMean equivalents of Treatment*Visit*Allergen and the comparisons would be the ratio of Active/Placebo within each Allergen strata within each visit. The same set of default posterior probability cut points will be used for each comparison.

Pharmacodynamic/Biomarker

Table 14 Default Posterior Probability (PP) cut-points of interest for Pharmacodynamic/Biomarkers analyses

Item	X = Treatment ratio (Active / Placebo) at each planned time point
1	PP(X<0.10) "More than a 90% reduction in mean response relative to Placebo"
2	PP(X<0.25) "More than a 75% reduction in mean response relative to Placebo"
3	PP(X<0.50) "More than a 50% reduction in mean response relative to Placebo"
4	PP(X<0.75) "More than a 25% reduction in mean response relative to Placebo"
5	PP(X<0.90) "More than a 10% reduction in mean response relative to Placebo"

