6	PP(X<1.00) "Any reduction in mean response relative to Placebo"
7	PP(X≥1.00) "Any increase in mean response relative to Placebo"
8	PP(X>1.10) "More than a 10% increase in mean response relative to Placebo"
9	PP(X>1.25) "More than a 25% increase in mean response relative to Placebo"
10	PP(X>1.50) "More than a 50% increase in mean response relative to Placebo"
11	PP(X>2.00) "More than a 2-fold increase in mean response relative to Placebo"
12	PP(X>10) "More than a 10-fold increase in mean response relative to Placebo"
Note: If the response is untransformed then the cut-points will be computed using the median of the posterior (adjusted) distribution for Placebo and the above ratios to determine the equivalent absolute difference (e.g. If Pbo median = 76 then Item 1 would be PP(Difference (A-P) < -68.4))	
Note: Shortened versions of the labels may be used in the TLFs as appropriate (e.g. PP(X<0.10) or PP(Any Reduction c.f. Pbo))	

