11.11 Appendix 11: Model Checking and Diagnostics for Statistical Analyses

11.11.1 Statistical Analysis Assumptions

Endpoint(s)	
 • All which are modelled using a Bayesian framework
Analysis	
 • Bayesian (Proc MCMC)

General Considerations for Bayesian Analyses (PROC MCMC):

The following points are for guidance and illustration and do not guarantee a successful model convergence. They cannot cover all eventualities and do not remove the requirement to do what is best for the specific set of observed data being modelled.

Priors:

Unless otherwise specified the following would be the default approach to selecting prior distributions:

- Non-informative priors of the form $\text{Normal}(0, \text{Var}=1\text{E}6)$ would be assigned to each fixed effect in the proposed statistical model.
- Non-informative Inverse-gamma priors of the form $\text{IGamma}(0.001, 0.001)$ would be assigned to stand-alone variance parameters that are not expected to take values near zero (e.g. for the residual variance rather than a random effect variance component)
- For stand-alone variance parameters that may take values close to zero a non-informative prior of the form $\text{Uniform}(0, \text{XXX})$ may be assigned for the SD
- For repeated measures models non-informative Inverse-Wishart priors will be assigned for the Variance Covariance matrix (VCV). They would use degrees of freedom equal to the dimension of the VCV matrix and an Identity matrix (of the same dimension).
- If there are issues with those variance parameters then the Identity matrix may be replaced with a diagonal matrix that uses best guesses for the residual variance at each repeated measure time point (or the residual estimates from fitting simple models)
- It is good practice to ensure that each prior distribution is visualised to ensure it appears sensible and allows clinically plausible response values, whilst not allowing impossible values to be drawn with high probability and that if it is intended to be non-informative it is doing so over the region of the likelihood function.

Note: There is no requirement to formally report these visualisation outputs.

Initial Values:

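### The fallback centre SD of 1000 leaves model-adjusted arm means for biomarkers and TNSS almost entirely to the prior, and makes placebo-based cut-points for untransformed endpoints unreliable

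*SAP*

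**What the plan says.** SAP 11.9.1 fits centre as a random effect by default. The standard deviation is meant to be chosen for each endpoint in turn: "Where possible historical data would be used to form a weakly informative prior for the SD, with the specific value described in the corresponding RAP". A fallback is then given: "If historical data are not available then the distribution for the random centre effects would use a SD value of 1000". That is one number for every scale.

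Only the LAR and EAR models state a centre prior (SAP 7.1.2 and 8.1.2). The sputum, blood, FeNO, nasal and serum sections (SAP 8.4.2.1 to 8.4.2.3) use models R1–R3, which contain centre, and give no centre value. TNSS borrows the FeNO model (SAP 9.1.1).

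SAP 11.11.1 gives a Normal prior with mean 0 and variance 1E6 that "would be assigned to each fixed effect in the proposed statistical model". It also has an optional alternative, which begins: "For stand-alone variance parameters that may take values close to zero a non-informative prior of the form". The alternative named there is Uniform(0, XXX) on the SD, and its bound is not stated.

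SAP 7.1.2 (Step 3) shows how to form an arm mean: intercept plus treatment, with centre dropped because its mean is zero. For biomarkers, SAP 8.4.2 asks for the equivalents of least-squares means by treatment and visit: "The posterior distributions of these quantities will be obtained and the median and 95% credible interval (equi-tail) will be tabulated and displayed graphically". The direct-challenge analyses (SAP 8.4.2.1.1, 8.4.2.1.4 and 8.4.2.2.1) also require back-transformed predictions for each arm and visit. The note to Table 14 adds: "If the response is untransformed then the cut-points will be computed using the median of the posterior (adjusted) distribution for Placebo". TNSS is planned untransformed.

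**The concern.** The data inform the sum of intercept and centre effect. They locate the intercept alone only if the centre effects are held reasonably close to zero. An SD of 1000 holds them nowhere near zero on a log2 scale or a 0–12 symptom score, and the intercept prior is just as wide. An arm mean read at a centre effect of zero therefore reflects mainly the two priors.

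At stake are the adjusted arm means and intervals planned as tables and figures for the biomarkers and TNSS. For untransformed endpoints, so are the probability statements whose thresholds are multiples of the placebo median. Discovering this at reporting would invite unplanned model changes after unblinding.

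**Working it through.** **The plan's own figure.** A cut-point for an untransformed response is (ratio − 1) × placebo median. The Table 14 example, with median 76 and ratio 0.10, gives 76 × (0.10 − 1) = −68.4, as printed. Any error in the placebo median therefore passes straight into the cut-point.

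**Inputs from the documents.** Centre SD 1000 (SAP 11.9.1); fixed-effect prior SD √1E6 = 1000 (SAP 11.11.1); six planned centres (SAP 7.1.2); 20 completers per arm (protocol 4.3); 20 ng arm as reference level (SAP 7.1.2); MCSE/SD below 0.01 for key parameters (SAP 11.11.1); about 100,000 draws (stated for the interim model, SAP 3.1).

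**Assumed.** Residual SD 2 (0.5 to 3 also run); TNSS means 4 on placebo and 3 on active; log2 means 5 and 4; TNSS as the sum of four 0–3 items, so 0–12. The check uses one visit. Visit terms are differences that the data identify, so they do not help to separate intercept from centre.

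**Posterior of the arm mean.** With J centres, the data fix each intercept-plus-centre sum very precisely relative to 1000. Combining the J centre priors with the intercept prior gives:

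- posterior SD = 1000/√(J + 1): 378 for J = 6, 447 for J = 4, 577 for J = 2;
- intercept mean = J/(J + 1) × the true value.

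An exact Gaussian posterior with 40 subjects reproduces these SDs. For J = 6 the result stays at 378 for residual SDs from 0.5 to 3, and with 48 subjects.

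- 95% half-width: 1.96 × 378 = 741 units. On log2 that is 741 × log10(2) ≈ 223 powers of ten in each direction.
- Because the intercept is the active arm, the placebo mean loses active mean/(J + 1). TNSS: 4 − 3/7 = 3.57. Log2: 5 − 4/7 = 4.43.

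**Monte Carlo error in the placebo median (TNSS).** The permitted MCSE is 0.01 × 378 = 3.8 units, a 13.7-fold error on log2. For a normal posterior, the error of the median is 1.2533 times that of the mean.

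| Setting | SE of median | 95% range of median | 25%-reduction cut-point (should be −1.0) |
|---|---|---|---|
| 100,000 independent draws | 1.5 | 0.6 to 6.5 | −0.16 to −1.63 |
| MCSE/SD at the 0.01 limit | 4.7 | −5.7 to 12.9 | +1.4 to −3.2 |

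At the limit, the placebo median is negative in about 23% of runs, which reverses the sign of the cut-points. Without simulation error the cut-point would be −0.25 × 3.57 = −0.89. Monte Carlo error therefore does most of the damage here. Items 6 and 7 use ratio 1.00, so their cut-point is zero whatever the median.

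**What survives.** The active-minus-placebo difference is −1.00, with posterior SD 0.640 at centre SD 1000 and 0.633 at centre SD 0.2. In an unbalanced layout the SDs are 0.667 and 0.634.

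**Remedies (J = 6, TNSS placebo mean).**

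- SD 1000 kept, arm mean averaged over fitted centres: 4.00, SD 0.45 (0.58 in the unbalanced layout).
- Centre SD 0.2, read at zero: 4.00, SD 0.46.
- Centre SD 1, read at zero: 4.00, SD 0.61.

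For comparison, the primary model's Gamma prior on the centre variance has mean 0.048 × 0.830 = 0.040, an SD of about 0.20 L.

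**The case against.** The rule that sets centre to zero is a worked example for the primary LAR model. SAP 8.4.2 asks only for least-squares-mean equivalents through suitable parameter combinations. A statistician who averaged over the fitted centres would meet no problem, and nothing forbids that. This stands as a point about under-specification. But nothing requires averaging either, and the one rule the SAP writes down leads to the bad result.

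The SAP also has safeguards. SAP 11.9.1 itself wants an SD suited to the endpoint. SAP 11.11.1 offers the Uniform prior, asks for priors to be visualised for plausibility, and lists re-scaling and re-parameterising among its remedies. An interval of ±741 would be noticed at the first run. These make a published error unlikely, but they do not withdraw the explicit value of 1000. The key convergence check can also pass, because it measures Monte Carlo error relative to a very large posterior SD.

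The consequences are bounded. The outputs are exploratory, sputum modelling depends on having enough data, and raw arm means with confidence intervals are reported separately in the descriptive tables and figures.

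Stronger readings are tempting but not supported:

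- That cut-points fail for biomarkers generally. Biomarkers are log2-transformed by default and use fixed ratios; only untransformed responses use the placebo median.
- That every TNSS probability statement is wrong. Items 6 and 7 are not affected.
- That the placebo median shrinks by one seventh of itself (14%). That factor applies to the intercept, which here is the active arm. In the example placebo moves by 3/7, or 11%.

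**Conclusion.** The point holds for model-adjusted arm means in the Bayesian sputum, blood, FeNO, nasal, serum and TNSS models. As written, their posterior SD is about 1000/√(J + 1), or 378 with six centres, so the tabulated, plotted and back-transformed arm means and intervals would be unusable. For TNSS, and any biomarker left untransformed, the Table 14 cut-points other than items 6 and 7 would be shifted by a multiple of one seventh of the active mean and dominated by simulation error.

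A reader might infer that treatment comparisons or the primary result are compromised. They are not: centre cancels from active/placebo ratios, differences and within-visit fold changes, and the LAR and EAR models have their own centre prior. The RNA model may be fitted by PROC MIXED, where the centre variance would be estimated.

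The conclusion assumes that no historical centre value is supplied later and that arm means follow the SAP 7.1.2 rule. The 378 and ±741 do not depend on the assumed residual SD over the range tried. The 3.57 and the cut-point ranges depend on the assumed TNSS means, and the first table row also assumes 100,000 independent draws.

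**What to change.** 1. In SAP 8.4.2, define each model-adjusted arm mean as intercept plus treatment and visit terms plus the average of the fitted centre effects. State the weighting of centres.
2. In the Table 14 note, take the placebo median from that quantity.
3. In SAP 11.9.1, replace the value of 1000 with a prior on the centre SD scaled to each endpoint's analysis scale, consistent with that section's own aim and the Uniform option in SAP 11.11.1. Justify the bound by endpoint and check sensitivity to it, since about six centres say little about a variance. The documents supply no bound, so none is proposed here.
4. State which of SAP 11.9.1 and 11.11.1 governs the centre term.

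The cost is SAP wording and a small change to the MCMC code, with no new data and no change to the primary analysis. It is best done before unblinding.

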
 A sensitivity analysis applying the final model to the mITT population may be performed Exploration of the relationship between treatment effect sizes and (potential) sub-populations based on eosinophil levels in blood: A model building exercise would take place using a similar strategy as that used to explore the importance of allergen exposure status. However, the base model will start with the simplifying assumption that allergen exposure is not necessary (i.e. use the M3 form of model). The base model will be compared to the fit of a model containing an additional term for the (log transformed if necessary and centered) absolute blood eosinophil from the Baseline visit (SV2, fitted as a continuous covariate). This is similar to model form M2 but with the continuous covariate taking the place of the allergen exposure term. Additionally the benefit of adding a term for the interaction between treatment and this continuous covariate will be explored (similar to the M1 form). If any model terms involving blood eosinophils are included in the model it will be used to predict the mean response for each treatment arm using the following blood eosinophil levels (values presented here may require transformation so they are incorporated into the model prediction on the appropriate scale): 100 cells/mL and 200 cells/mL. Also the treatment difference at each of those eosinophil levels should be evaluated. Non-informative priors would be used for the parameters representing these additional term(s). To produce the descriptive summary tables the blood eosinophil variable will be grouped and summarized by the categories described in Section 11.9.1. Note: If data permit the allergen exposure status may also be added to the model (although there may not be sufficient subjects to estimate the required number of model 			

Primary Statistical Analyses

parameters; especially when trying to estimate the multi-way interactions involving treatment, allergen exposure and eosinophil levels).

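### Blood-count thresholds in the SAP are printed per mL where the numerals make sense only per microlitre, which would empty one descriptive eosinophil subgroup and misplace the conditional predictions and one set of laboratory flags

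*SAP*

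**What the plan says.** Three parts of the SAP state blood-cell thresholds per millilitre.

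- **Section 11.9.1** labels the covariate "Blood Eosinophil Levels (Cells/mL" and defines two categorical versions: "Baseline (SV2) Blood Eosinophils: <150 Cells/mL and >= 150 Cell/mL" and "BAC visit Blood Eosinophil Levels: <150 Cells/mL and >= 150 Cell/mL".
- **Section 7.1.2** fits blood eosinophils as a continuous covariate, alone and in interaction with treatment. If any eosinophil term is kept, arm means and the treatment difference are predicted at "100 cells/mL and 200 cells/mL". A note adds that "values presented here may require transformation so they are incorporated into the model prediction on the appropriate scale". The descriptive tables use the 11.9.1 categories. Section 8.1.2 extends the exercise to EAR and reuses the same prediction values in the repeated-measures models.
- **Section 11.7.1** gives absolute limits of potential clinical importance for "Eosinophils (K/mL" (above 0.6), "Monocytes (K/mL" (below 0.1 or above 0.9) and "Basophils (K/mL" (above 0.9).

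Neither document gives a blood count per microlitre, a conversion rule, or the unit in which the central laboratory reports.

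**The concern.** Blood eosinophils ordinarily number tens to hundreds per microlitre, so thresholds of 100, 150 and 200 suit a per-microlitre count and lie far below any plausible per-millilitre count. The three sections also agree with one another: 0.6 K/mL is 600 cells/mL, four times the 150 cut-off. A programmer who converts the laboratory data to the printed unit would therefore meet no contradiction inside the SAP.

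At stake are the descriptive split by eosinophil level, the predictions meant to show the treatment effect at a lower and a higher eosinophil level, and the haematology listings of potentially important values. Listings 25 and 26 are assigned to the external service provider, whose programmers work from the SAP text.

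**Working it through.** The SAP derives no figure here, so there is none to reproduce. The check is a unit conversion and its consequences.

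**Conversion** (1 mL = 1000 microlitres; K = 1000 cells)

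| SAP section | As printed | Cells per microlitre |
|---|---|---|
| 7.1.2 | 100 and 200 cells/mL | 0.1 and 0.2 |
| 11.9.1 | 150 cells/mL | 0.15 |
| 11.7.1, eosinophils | 0.6 K/mL = 600 cells/mL | 0.6 |
| 11.7.1, monocytes | 0.1 and 0.9 K/mL | 0.1 and 0.9 |
| 11.7.1, basophils | 0.9 K/mL | 0.9 |

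**Assumption.** Eosinophil counts of about 50 to 500 per microlitre, that is 50,000 to 500,000 per mL. The conclusion hardly depends on this range: 1 eosinophil per microlitre is 1,000 per mL, already above both 150 and 600.

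**Subgroup split (Tables 2.2 and 2.11).** The lowest assumed count is 50,000 / 150 = 333 times the cut-off, so nobody is in the low group. As a second check, take a log-normal count with assumed median 100 to 400 per microlitre and log-SD 0.5 to 0.8. The probability of a value below 150 per mL is then at most 2e-16. Read per microlitre, the probability of a value below 150 is 0.02 to 0.79, or about 1 to 32 of the 40 planned completers, so the same numeral does separate subjects.

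**Prediction points (Tables 2.6, 2.9, 2.13 and 2.15, if an eosinophil term is kept).**

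- Log scale: log2(50,000 / 100) = 9.0 and log2(500,000 / 100) = 12.3, so the lower point sits 9 to 12 doublings below the assumed range. Under the log-normal assumptions the two points lie 7.8 to 16.6 SD below the median. Read per microlitre, they lie between 2.8 SD below and 1.4 SD above it.
- Untransformed scale: the points are 0.1 and 0.2 cells per microlitre. They differ by 0.1 cell, so both predictions are in effect made at zero eosinophils and nearly coincide.

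**Alert limits (Listings 25 and 26).** The lowest assumed eosinophil count is 50,000 / 600 = 83 times the upper limit, so essentially every subject is flagged high. Monocytes would most likely be flagged too, since any count above 0.9 per microlitre exceeds the limit. A basophil count recorded as zero would not be flagged. Read per microlitre, the log-normal probability of exceeding 0.6 K is 0 to 0.31.

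**What the unit does not touch.** Multiplying the covariate by 1000 adds log2(1000) = 9.97 to every log2 value, and centring removes it. Untransformed, it divides the slope by 1000 under a near-flat prior (variance 1E6, SAP 11.11.1). The comparison of models with and without the eosinophil and interaction terms is essentially the same either way.

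**Using the numerals unconverted is not always safe.** Suppose the laboratory reports in 10^9/L (an assumption). The 0.6 and 0.9 limits then work as they stand. The assumed counts, however, become 0.05 to 0.5, all below 150, so the high group is empty instead.

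**The case against.** The strongest reply is that this is a unit label and no calculation in the SAP is wrong. The numerals are sensible per microlitre, no text tells anyone to convert data to cells/mL, and an empty subgroup would be noticed. SAP 11.9.1 allows small categories to be refined before unblinding, and 7.1.2 allows the prediction values to be transformed. Much of this stands: a labelling slip is the likeliest explanation, and an attentive statistician could well catch it. But the refinement clause concerns small subgroups and the transformation note concerns the model scale. Neither mentions a unit.

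The reply is also right about scope. The 150 split is descriptive. The predictions are conditional, and an erratic treatment difference further needs a retained interaction. The outputs are sensitivity analyses of second delivery priority.

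A reader might infer three stronger things that the documents do not support:

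- **That the question of effect modification by eosinophils is spoiled.** It is judged on a continuous covariate, which the unit essentially does not affect.
- **That the safety review would miss abnormalities.** Only three limits are in K/mL. The other haematology limits are multiples of the laboratory range or separate MCV and MCH limits. The Appendix 13 specification for the emergent haematology table uses normal ranges, although the overview in 8.2.2 still refers to the PCI criteria. Over-flagging lengthens the listings but removes no value.
- **That the primary result is at risk.** It uses neither the split nor the prediction points.

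A micro sign lost in converting the PDF to text cannot be excluded. It is less likely because the sign is legible for bilirubin in the same section.

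**Conclusion.** The point holds as a unit error in analysis thresholds, by a factor of exactly 1000 against the same numerals per microlitre. Its reach is one empty group in two descriptive tables, unusable predictions in four conditional sensitivity tables and their figures, and an uninformative eosinophil flag (most likely a monocyte flag too) in two listings.

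The printed units are certain as far as the SAP text shows. That they are too small rests on general knowledge of blood counts, and the consequences arise only if the text is applied as written. It should be corrected before these outputs are programmed, but it gives no reason to doubt the main efficacy conclusions.

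**What to change.** Check the printed unit against the source PDF and the central-laboratory data-transfer specification. Then correct SAP 7.1.2 (100 and 200), 11.9.1 (150, in the label and both categories) and 11.7.1 (monocytes, eosinophils, basophils). Cells per microlitre and K per microlitre appear to be what was meant. Beside each cut-off, print the unit in which the laboratory data arrive and the conversion, so that the numeral can be applied without inference. While doing so, align the 8.2.2 overview with the Appendix 13 specification on whether the emergent haematology table uses normal ranges or PCI limits.

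The cost is SAP wording only: no new data, no change of design, and no change to the models.
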